Protocol Title: Wearable Bioimpedance Analyzer for Tracking Body Composition Changes: A Randomized Controlled Trial

Protocol Version: 1.1

Protocol Date: 8/1/22

Principal Investigator: [name], PhD

Research Team: [name], [name], [name]

1) Abstract

- a) Obesity, namely at body mass index (BMI) levels exceeding $40\text{kg}/\text{m}^2$ (class III obesity), is a risk factor for many diseases including osteoarthritis (OA). In arthroplasty, patients in this population frequently present for and are turned away from surgical intervention. Subsequently, efforts are made to decrease BMI through simple weight loss, yet these have been suggested as ineffective and counterproductive. Furthermore, simple weight loss may include muscle mass loss, which is an additional risk factor for surgery. In our clinic, efforts have been made to encourage muscle mass gain and body fat loss over simple weight loss where progress has been tracked through stationary, multi-frequency bioimpedance analysis (BIA). BIA is a readily available technology offered to industry and consumers, and BIA has recently been incorporated into wearable devices. In our department, a novel clinic aimed at holistically serving the osteoarthritic-class III obese population for controlled and monitored weight loss through BIA.

This study, a randomized controlled trial, aims to recruit adult patients with class III obesity presenting to the arthroplasty-obesity clinic. While all patients will receive individual body composition coaching to increase muscle mass and decrease body fat mass, they will be randomized to one of two cohorts: the study group will receive a wearable BIA wristband (InBody BAND 2) and instruction on its use in addition to the standard coaching, and the control group will only receive the standard coaching.

This study aims to identify if the use of a wearable BIA wristband aids in the desired body composition changes. In addition, this study aims to quantify the body composition changes exhibited by each cohort. Finally, this study aims to track surgical outcomes for those patients that are indicated for total joint arthroplasty.

2) Background and Significance/Preliminary Studies

- a) Obesity is a well-known epidemic in the US with prevalence nearing 40%. [1] Obesity is a risk factor for a myriad of disease states including osteoarthritis (OA) due to increased load on the weightbearing joints. Therefore, patients with obesity, and namely those with body mass index (BMI) approaching $>40\text{kg}/\text{m}^2$ (class III obesity), suffer from OA disproportionately compared to their non-obese peers. [2] As this population frequently reports to arthroplasty clinics, studies have identified increased rates of post-operative complications following total joint arthroplasty (TJA) specifically in the class III obese population. [2-5] To combat this increased risk, arthroplasty surgeons traditionally have excluded this population from their surgical practice or encouraged their patients to lose weight in order for their BMI to drop below $40\text{kg}/\text{m}^2$; however, these practices have been recently questioned. [6-8]

With the validity of lowering BMI to improve TJA outcomes being questioned, studies have made efforts to identify more patient-specific factors such as body composition. Body composition can be identified through several modalities including anthropomorphic measurements, DEXA, MRI, and CT. [9-11] In addition, bioimpedance

analysis (BIA) offers rapid, accurate, and non-invasive assessment without the use of ionizing radiation. [9, 12, 13] BIA can be completed through multiple devices including a stationary, scale-like device, a portable ECG-like device, or even wearable wristbands.

Our group has conducted numerous studies focusing on body composition in arthroplasty patients, including changes they experience following surgery and pre-operative risk identification. By employing both clinic-based and home-based assessments more frequently than patients would normally have, this study aims to identify any benefit, if any, a wearable BIA device serves in an obese-arthroplasty population.

3) Study Aims

- a) Aims:
 - i) To identify if the use of a wearable BIA wristband aids in the desired body composition changes (body mass loss, fat mass loss, skeletal muscle mass gain)
 - ii) To quantify the body composition changes exhibited by each cohort
 - iii) To track surgical outcomes for those patients that are indicated for total joint arthroplasty
- b) Hypotheses:
 - i) The wearable group will exhibit the desired body composition changes more rapidly than the control group
 - ii) The wearable group will exhibit greater desired body composition changes more rapidly than the control group
 - iii) The wearable group will less post-operative complications than the control group

4) Administrative Organization

- a) This study will solely be completed at the University of Iowa Healthcare and Clinics Department of Orthopaedics and Rehabilitation.

5) Study Design

- a) Experimental design of the study: randomized controlled trial with single blinding
- b) Study population general description
 - i) Specify total number of adult subjects, age range and percent by gender
 - (1) 90 subjects (>18 years old)
 - (2) 50% male, 50% female
 - ii) Specify total number of minor subjects (less than 18 years of age), age range and percent by gender.
 - (1) none
- c) Sample size determination and power analyses
 - i) A power analysis was performed by the orthopedic department statistician [name].
- d) Study outcomes/endpoints
 - i) Primary outcomes
 - (1) Muscle mass, body mass, and fat mass changes from baseline at 3-, 6-, 9-, and 12-months
 - ii) Secondary outcomes
 - (1) Time to achieve desired body composition changes
 - (2) Time to TJA indication
 - (3) Surgical outcomes for those that undergo TJA

6) Study Procedures

- a) Describe Subject selection procedures
 - i) Describe the sampling plan including Inclusion/Exclusion criteria (subject and disease characteristics)
 - (1) Inclusion Criteria
 - (a) Adults > 18 years
 - (b) BMI > 40kg/m2
 - (c) Presenting to arthroplasty-obesity clinic with desire for total joint arthroplasty procedure
 - (d) Owns a smartphone capable of handling iOS or Google Play apps
 - (2) Exclusion Criteria
 - (a) Has a pacemaker or other electronic pacemaker placement
 - (b) Inability to complete study protocols
 - (c) Inability to stand unsupported for 60-90 seconds
 - ii) Indicate if the study plans to enroll non-English speaking subjects. If so, specify language(s), who will translate documents, who will serve as a translator. The IRB must review and approve all translated documents.
 - (1) This group will not be enrolled
 - iii) Indicate if the study will enroll subordinates of the PI or a member of the research team.
 - (1) This group will not be enrolled
 - iv) Indicate if the study will enroll pregnant women for research on fetuses and neonates
 - (1) This group will not be enrolled
 - v) Indicate if the study will enroll adult subjects who have cognitive impairment and are not able to provide legally effective informed consent. If so, specify how you will assess capacity to consent and whether you will enroll subjects who cannot consent for themselves. Describe the consent process with the Legally Authorized Representative.
 - (1) This group will not be enrolled
 - vi) Indicate if the study will enroll subjects whose capacity to consent may change during the study. If so, specify how you will assess capacity to consent and how you will obtain consent from subjects or their Legally Authorized Representative.
 - (1) This group will not be enrolled
- b) Describe all possible recruitment procedures
 - i) Describe all recruitment methods and materials.
 - (1) Subjects reporting to arthroplasty-obesity will be recruited by the study team members using the informed consent form as materials
 - ii) Specify if the researcher will use protected health information (PHI) to identify potential subjects – what data elements, why you couldn't recruit without accessing PHI, why you couldn't obtain patient permission, how you will protect identified PHI used for recruitment purposes, when you will remove identifiers OR justification for storing identifiers until the end of the recruitment period. You must agree to agree not to reuse or disclose this information.
 - (1) The subjects will be identified by those reporting to arthroplasty-obesity clinic, which the PI has access to. The identifiable information used will be the patient's name, age, BMI, and reason for reporting to clinic.
 - iii) Describe screening prior to consent

- (1) Patients' medical record will be reviewed for their age, BMI, and reason for reporting to clinic. When they are approached, they will be asked if they have a smartphone and/or an electronic cardiac device.
- iv) What recruitment materials will be provided to the potential participant (brochures/information sheets/video presentation)?
 - (1) The informed consent will be used.
- v) Specify if you are discussing study in person or by phone prior to consent.\
 - (1) This will be discussed in person.
- c) Indicate where and when consent be obtained
 - i) State who will conduct the consent process
 - (1) Any member of the study team will conduct the consent process
 - ii) Describe the steps of the consent process in detail.
 - (1) The patient will be identified on the clinic schedule, and they will be approached in their private clinic room. They will be asked if they are interested in participating in a study. If they agree, they will be asked the above screening questions. If they are eligible a study team member will orally review the consent form and have the participant review the written consent form. All questions will be answered.
 - iii) Specify what documents will be used in the consent process (Informed Consent Document, Consent Letter or Information Sheet, Assent Document, Verbal/Phone Script, Exempt Information Sheet, Consent Summary, Other)
 - (1) Informed consent form
 - iv) Specify if the study requires a waiver of consent OR waiver of documentation of consent. If so, provide justification.
 - (1) No waiver
 - v) Specify how long subjects can consider whether to participate AND if they can consult with other people before deciding to participate.
 - (1) They will be eligible until the end of their initial clinic visits to arthroplasty-obesity clinic
 - vi) Specify how long after subjects agree to participate before the study procedures begin.
 - (1) Immediately
- d) Describe screening procedures
 - i) Describe eligibility screening procedures before and/or after consent.
 - (1) Subjects will be asked about owning a smartphone and if they have an electronic cardiac device prior to the consent process
 - ii) Describe the screening schedule (number of visits, length of visits)
 - (1) The screening visit will be at the enrollment visit
 - iii) Indicate whether screening tests/procedures are part of standard care or done for research purposes only
 - (1) These are done per research protocol
 - iv) Specify what happens with screen failures (including any data gathered during screening)
 - (1) They will not be eligible to enroll, and no information/PHI will be recorded.
- e) Describe randomization procedures (if applicable) – Specify the randomization scheme and process.

- i) Block randomization in RedCap. Patients will be randomized at the conclusion of their clinic visit as to not influence the education they receive by the PI/provider
- f) Describe study intervention(s)
 - i) For Other types of intervention studies, describe:
 - (1) Active intervention description
 - (a) Patients will be provided a BIA wearable (InBody BAND 2) and instructions regarding downloading smartphone app. Education regarding the device and app will be provided. In addition, they will receive the standard procedures/education provided in arthroplasty-obesity clinic
 - (2) Control group
 - (a) They will receive the standard procedures /education provided in arthroplasty-obesity clinic
- g) Describe all study assessments and activities
 - i) Provide a thorough, detailed description
 - (1) Randomization
 - (a) Once enrolled, patients will be randomized by a non-PI study member. Randomization will occur after the clinic standard education as to not be influenced based on randomization group.
 - (2) All patients
 - (a) All patients will experience a “coaching” period and be eligible for a “surgical period”. All patients (study and control) will undergo the clinic standard operating procedures of stationary BIA, hand-grip strength, and exercise and nutritional education (weight/resistance training, low carbohydrate/high protein diet) in the “coaching” period. All patients will also be advised of the goal to maintain or lose body mass, lose body fat, and gain muscle mass, which is also clinic standard operating procedure. Patients will follow-up in the clinic per standard protocol at approximately every 3 months (± 1 month). At each visit, stationary BIA, hand-grip strength, and exercise and nutritional coaching will be repeated, as is standard in clinic. All patients will be eligible to be indicated for TJA at the PI’s discretion. Per clinic procedures, patients are indicated for TJA as they achieve their body composition goals (maintain or lose body mass, lose body fat, and gain muscle mass). All patients will be instructed to not discuss their study arm (wearable or control) with the PI. Patients are eligible to enter the surgical period at any point during the coaching period. If patients feel that they meet their goals prior to they are eligible to reschedule their appointment sooner than the next visit. All patients will receive a phone call from a study team member every 1 month to assess compliance with study arm and check in on perceived progress.
 - (3) Wearable group
 - (a) If patients are randomized the wearable group, they will be provided a wearable and instructions on installing the app and its features. They will be instructed to take BIA measurements at least weekly via the wearable. The wearable group will be instructed at the beginning of each visit to remove and keep their wearable out of sight of the PI during their visit.
 - (4) Patients who enter “Surgical” period

- (a) Patients who are indicated for TJA (at the PI's discretion) will leave the coaching period and enter the surgical period. Patients' medical record will be followed if they are indicated for TJA for post-operative outcomes such as infection, reoperation, implant failure. Surgical follow-up will occur for up to 24 months following study enrollment.
- ii) Provide a schedule of all study assessments and subject activities, including a tabular representation or timeline as applicable
 - (1) See **Table I** below
- h) Recontacting Subjects Lost to Follow Up – Indicate if the researcher will attempt to locate subjects if the research team is unable to reach them through the contact information they provided. Describe the procedures and justification for these efforts to locate subjects.
 - i) Research members will not contact the patients lost to follow, as standard clinic procedures have nursing staff contact the patients.
- i) Subject Compensation
 - i) Specify compensation method(s)
 - (1) Patients will not be compensated monetarily. Those randomized to the study cohort will be able to keep their wearable device, if desired.
 - ii) Describe the compensation plan, including amount per visit, total compensation amount, pro-rating for early withdrawal
 - (1) N/A
 - iii) Indicate whether the study will use the departmental cash handling plan or obtain approval from Accounting Services for a study-specific cash handling plan.
 - (1) N/A

7) Privacy and Confidentiality Protections

- a) Describe privacy protections – collecting data in a private space, collecting the amount and type of information you need to answer your research question(s)
 - i) Only the minimum necessary data will be collected. The data collected will be done in a private clinic room.
- b) Describe plans and justification for collecting social security number (SSN)
 - i) N/A
- c) Confidentiality / Data Security Plans – Refer to the Data Security Educational Tool and the Protecting Sensitive Data page of the UI ITS website. Specify plans for transmitting, transporting and/or storing:
 - i) Paper records
 - (1) Informed consent documents to be kept in PI's locked office
 - ii) Electronic records - Specify who is responsible for maintaining security. Researchers are advised to consult with the departmental IT representative to establish a data security plan that is appropriate to the level of security of the data being collected/stored for the project.
 - (1) Standard protections on departmental server
 - iii) Biospecimens - Specify who is responsible for maintaining security.
 - (1) N/A
- d) Plans for sharing data or taking data outside the UI
 - i) N/A

8) Risks and Benefits

- a) Describe all possible risks (physical, emotional or psychological, financial, legal or social risks).
 - i) Risks include loss of information/privacy, falling off stationary BIA scanner, hand pain from hand grip strength testing.
- b) Describe all steps to minimize any possible risk to subjects.
 - i) Data will only be accessed by need-to-know study members, a study team member will supervise and “spot” the subject on the stationary BIA scanner, patient will be advised to take rests in between hand grip strength testing to minimize pain.
- c) Describe all guaranteed direct benefits to subjects (do not include compensation or hypothesized results).
 - i) None
- d) Describe potential benefits to society from the results of the research.
 - i) Future patients will benefit from knowing if wearable technology has an effect or not.

9) Safety Monitoring Plan

- a) N/A

10) Data Analysis Plan

- a) Describe statistical analysis methods as appropriate. Consult with a biostatistician, if appropriate. The analysis plan should correspond with the data collection described in the Study Procedures section. Describe plans for intent-to-treat methodology and any sample stratification.
 - i) Noninferiority comparison of the primary outcome and secondary outcome between the treatment groups at each time points.
 - ii) Multivariate analysis to compare patient demographics between the two treatment arms.
 - iii) Non-parametric tests such as ANOVA and ANCOVA will be utilized to determine if there is any difference between the two groups.
- b) Provide the rationale or power analysis to support the number of subjects proposed to complete the study.
Group sample sizes of 44 in the treatment and control arm achieve 80% power to detect a difference of 1.676 in a design with 5 repeated measurements having a compound symmetry covariance structure when the standard deviation is 3.610, the correlation between observations on the same subject is 0.500, and the alpha level is 0.050

11) Tables and Figures

Table I. Schedule of study procedures.

Study Period	Coaching ^a													Surgical ^a
	V1	V2	V3	V4	V5	V6	V7	V8	V9	V10	V11	V12	V13	
Visit Number	0	1	2	3	3	4	6	7	8	9	10	11	12	Until Month 24
All Patients														
Screening	X													
Consent	X													
Randomization	X													
Clinic Education ^b	X			X			X			X				X
Stationary BIA ^b	X			X			X			X				X
Handgrip Strength ^b	X			X			X			X				X
Phone Visit		X	X		X	X		X	X		X	X		
Wearable Group														
Wearable Distribution	X													
Wearable Compliance Check		X	X	X	X	X	X	X	X	X	X	X	X	
Surgical Outcomes Check^c														
^a Patients may exit the Coaching period and enter the Surgical period at any time point														
^b Standard protocol for all patients presenting to arthroplasty-obesity clinic														
^c Only for study group														
^d Only for subjects that undergo TJA. Will occur via EMR rather than direct patient contact.														

12) Literature Citations

1. Obesity: preventing and managing the global epidemic. Report of a WHO consultation. World Health Organ Tech Rep Ser 894: i, 2000
2. Obesity and total joint arthroplasty: a literature based review. In: J Arthroplasty. United States: 2013 Elsevier Inc. 714. 2013

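### Complications compared only among patients who reach TJA are not a randomised comparison, and the plan states no assumption that would let a difference be attributed to the wearable

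*Combined protocol and SAP*

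**What the plan says.** - **Outcome.** Section 5(d)(ii)(3) lists "Surgical outcomes for those that undergo TJA". The restriction to operated patients comes from this line.
- **Hypothesis.** Section 3(b)(iii): "The wearable group will less post-operative complications than the control group". The matching aim, 3(a)(iii), is milder: it only tracks surgical outcomes in patients indicated for TJA.
- **Analysis.** Section 10(a)(i): "Noninferiority comparison of the primary outcome and secondary outcome between the treatment groups at each time points". Surgical outcomes are not exempted, and no margin is given.
- **Entry to surgery.** Randomisation takes place at the end of the first clinic visit (section 6(e) and Table I). After that, under section 6(g)(i)(2), "patients are indicated for TJA as they achieve their body composition goals", at the investigator's discretion. The same section adds: "Patients are eligible to enter the surgical period at any point during the coaching period".
- **Expected effect on entry.** Hypothesis i: "The wearable group will exhibit the desired body composition changes more rapidly than the control group". Time to TJA indication is itself a secondary outcome, so the protocol treats entry to surgery as something the device may affect.
- **Follow-up.** Section 6(g)(i)(4): "Surgical follow-up will occur for up to 24 months following study enrollment".

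**The concern.** Randomisation makes the two arms comparable at the first visit. It does not make the operated patients of one arm comparable with those of the other, because they are selected later by a process that the intervention is meant to influence. If hypotheses i and ii are true, the wearable changes who is operated on, and when. A device that brings higher-risk patients to surgery would then appear to cause complications. One that brings additional lower-risk patients would appear protective. Neither result would need any effect on any patient's complication risk.

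The plan names no estimand, adjustment or sensitivity analysis for this selection. The template prompt in section 10(a) asks for intent-to-treat plans, and the answers give none. At stake is a published statement that the wearable reduces, or does not worsen, surgical complications, resting on a comparison that cannot carry it.

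**Working it through.** **1. The plan's own figure.** Section 10(b) gives 44 per arm for 80% power: difference 1.676, SD 3.610, 5 measurements, correlation 0.500, alpha 0.050. For a time-averaged difference under compound symmetry:

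- Effective SD = 3.610 × √((1 + 4 × 0.5)/5) = 3.610 × √0.6 = 2.796.
- n = 2 × (1.960 + 0.842)² × 2.796² / 1.676² ≈ 43.7, so 44 per arm (two-sided). Power at 44 is 80.3% by the normal approximation and 79.4% with the t distribution.

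The figure reproduces. It concerns a repeated continuous measurement, not complications, for which no sample size is given.

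**2. Selection with no device effect on risk.** The documents give no TJA or complication rates, so the following are assumptions:

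- a = 30% of patients would reach TJA in either arm, with complication risk 8%.
- b = a further 10% to 30% reach TJA only with the wearable, with complication risk r between 4% and 16%.
- The wearable changes no patient's complication risk.

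The control risk among operated patients is 8%. The wearable risk is (a × 8% + b × r)/(a + b). The ratio therefore equals 1 + [b/(a + b)] × (r/8% − 1).

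| b | r | Wearable risk, operated | Ratio to 8% |
|---|---|---|---|
| 10% | 4% | (2.4% + 0.4%)/0.40 = 7.0% | 0.875 |
| 10% | 16% | (2.4% + 1.6%)/0.40 = 10.0% | 1.25 |
| 20% | 4% | (2.4% + 0.8%)/0.50 = 6.4% | 0.80 |
| 20% | 16% | (2.4% + 3.2%)/0.50 = 11.2% | 1.40 |
| 30% | 4% | (2.4% + 1.2%)/0.60 = 6.0% | 0.75 |
| 30% | 16% | (2.4% + 4.8%)/0.60 = 12.0% | 1.50 |
| any | 8% | 8.0% | 1.00 |

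The ratio depends only on the share of added patients among those operated on in the wearable arm, and on their risk relative to the others.

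**3. Precision.** With 45 per arm (half of 90), these rates give 13.5 operated controls and 18 to 27 operated wearable patients. At 13.5 and 27, with 8% risk in both, the 95% half-width for the difference is 1.96 × √(0.08 × 0.92 × (1/13.5 + 1/27)) = 0.177, about 18 percentage points. The approximation is rough, because only 13.5 × 8% ≈ 1 control event is expected.

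**4. Follow-up time.** If surgery took place at indication (an assumption), indication at month 3 leaves up to 24 − 3 = 21 months of observation and indication at month 12 leaves 24 − 12 = 12. At an assumed constant rate of 0.005 per month, the cumulative risks are 1 − e^(−0.105) = 10.0% and 1 − e^(−0.060) = 5.8%, a ratio of about 1.7. This is the widest contrast between scheduled 3-monthly visits. It shrinks if complications cluster soon after surgery.

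**5. Denominator of all randomised patients.** Under the rates in step 2, the proportion with TJA and a complication is 30% × 8% = 2.4% in controls. In the wearable arm it runs from 2.4% + 10% × 4% = 2.8% to 2.4% + 30% × 16% = 7.2%. This measure keeps the randomisation, but it rises simply because more patients are operated on.

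**The case against.** **The aim is descriptive.** Aim iii only tracks outcomes. Section 10(a)(i) speaks of a single secondary outcome at time points, while surgical outcomes have no scheduled ones and no margin is stated. This stands in part: a noninferiority claim on complications is a reading of 10(a)(i), not an explicit plan. But hypothesis iii is directional and nothing exempts surgical outcomes, so an analyst following the text could test them.

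**Hypothesis iii does not mention operated patients only.** Correct. A reader might infer that the hypothesis itself imposes the restriction. It comes from the outcome definition, and from the fact that a post-operative complication requires an operation.

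**The investigator is masked and both arms share the same goals.** Patients are told not to discuss their arm and to keep the device out of sight. This limits indication that depends on knowing the arm. It does not remove selection through body composition, which the device may change.

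**The bias is small beside the noise.** In the illustration it is at most 12% − 8% = 4 percentage points, against a half-width of about 18. That is a reason for modest severity, and a further reason to describe rather than test. It does not make the comparison valid.

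**Table I.** A reader might infer from the note "Only for study group", whose marker appears on the surgical outcomes row, that complications are checked in one arm only. The documents do not support that. The next note, on subjects who undergo TJA and record review, plainly describes this row yet is attached to none, so a misplaced letter or an extraction fault is likely. Section 6(g)(i)(4) follows patients indicated for TJA without regard to arm.

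**Conclusion.** The concern holds. As planned, the complication comparison is between groups formed after randomisation by a process the wearable is hypothesised to alter, with observation time that can also differ by arm. Attribution to the wearable would need an added assumption, such as no effect of the device on who reaches TJA, or a principal-stratum analysis. The plan offers neither.

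The size is unknown. The range of 0.75 to 1.50 rests on assumed rates and on the assumption that the wearable only adds patients to surgery. It shows that selection alone can move the ratio in either direction, not how far it will move here. A reader might infer that any observed difference must be spurious. That goes too far: there is no selection distortion if the added patients carry the same risk as the others.

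This is one unpowered secondary outcome. The change should be made, but the body-composition comparison does not depend on it.

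**What to change.** 1. In section 10(a)(i), exclude surgical outcomes from the noninferiority comparison.
2. Report complications among operated patients by arm with confidence intervals and time since surgery, labelled as description and not as an effect of the wearable.
3. Report the proportion with TJA by a fixed time, chosen in advance, with all randomised patients in each arm as denominator. Time to TJA indication, already listed, is related but does not give this figure.
4. If the proportion with TJA and a complication is also reported over all randomised patients, state that it answers a different question and read it beside the TJA proportion.
5. Ascertain TJA from the medical record for every randomised patient up to the fixed time. Section 6(g)(i)(4) follows records only for those indicated, and the coaching schedule stops at month 12.
6. Reword hypothesis iii to match.

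The cost is protocol wording and a small amount of extra record review, with no added visits. The sponsor gives up a causal claim on complications that this design cannot support.

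### Patients' own use of a body-composition device is neither screened for nor recorded, and no visible text asks controls not to start one, so a null result could be hard to interpret

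*Combined protocol and SAP*

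**What the plan says.** - **Eligibility, section 6(a)(i).** Inclusion requires an adult with BMI above 40 who wants joint replacement and who meets the criterion "Owns a smartphone capable of handling iOS or Google Play apps". The exclusions are a pacemaker, being unable to follow the protocol, and being unable to stand unaided for 60 to 90 seconds. None concerns a device that the patient already uses.
- **Screening, sections 6(b)(iii) and 6(d)(i).** Patients are asked about a smartphone and an electronic cardiac device, and about no other device.
- **Arms, section 6(f)(i).** The active arm gets the band, the app and education on both, and in addition "they will receive the standard procedures/education provided in arthroplasty-obesity clinic". The control entry consists of that last element alone. The abstract likewise limits controls to standard coaching.
- **Monitoring, section 6(g)(i)(2) and Table I.** A study team member calls every patient monthly about adherence to the allocated arm and perceived progress. What a control is asked is not described. The wearable compliance row of Table I is in the wearable-group block.
- **Availability, abstract.** "BIA is a readily available technology offered to industry and consumers, and BIA has recently been incorporated into wearable devices".
- **Analysis, section 10.** The power statement makes no allowance for device use by controls, and the analysis plan does not say how such use would be handled.

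**The concern.** Aim i asks whether using the wristband helps patients reach the desired body composition. That needs a difference in exposure between the arms. Every participant owns a suitable phone, every participant is coached toward the same goals, and section 6(g)(i)(2) links indication for surgery to reaching them. Patients know their arm, since they are asked to keep it from the PI. A control therefore has both the means and a motive to track body composition at home.

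Two routes could narrow the contrast. A control may start using a device after randomisation. Or a patient in either arm may already use one at enrolment, so that allocation changes little for that patient. Neither would show in the trial's data. A null result could then mean that the band does not help, or that controls had something like it.

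Lost power is not the only consequence. Section 10(a)(i) plans a noninferiority comparison without a margin or a stated direction. Pulling the arms together makes noninferiority easier to meet when the tested arm is truly the worse one, which is when the test ought to fail.

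**Working it through.** **Inputs, all from section 10(b).** The design is said to "achieve 80% power to detect a difference of 1.676" with 44 per arm, where "the standard deviation is 3.610", "the correlation between observations on the same subject is 0.500" and "the alpha level is 0.050", over 5 repeated measurements with compound symmetry. Sidedness is not stated. The outcome and units of the difference are not stated either, but the power calculation does not need them.

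**Step 1: reproduce the plan's figure.**
- SD of a patient's average over 5 measurements: 3.610 × √((1 + 4 × 0.5)/5) = 3.610 × √0.6 = 2.796.
- Standard error of the difference: 2.796 × √(2/44) = 0.596.
- Power, two-sided 5%: Φ(1.676/0.596 − 1.96) = 80.3% (79.4% with the noncentral t).
- Required size: 44 per arm two-sided, which matches the plan. A one-sided test would need 35, so the plan's figure is two-sided.

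**Step 2: find the slack.** Section 5(b) plans 90 patients against 2 × 44 = 88. The 2 spare patients are 2/90 = 2.2% of enrolment, and no allowance for contamination is stated.

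**Step 3: dilute the contrast.** Let c be the net share of the contrast lost. The difference becomes 1.676 × (1 − c), and power is Φ(1.676 × (1 − c)/0.596 − 1.96). The documents give no value for c, so it is an assumption shown over a range.

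| c | Difference | Power at 44 per arm | Per arm for 80% |
|---|---|---|---|
| 0 | 1.676 | 80.3% | 44 |
| 5% | 1.592 | 76.1% | 49 |
| 10% | 1.508 | 71.6% | 54 |
| 20% | 1.341 | 61.4% | 69 |
| 30% | 1.173 | 50.3% | 90 |

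**Step 4: relate c to the share of users.** If a share u of controls uses a device that delivers a fraction f of the band's effect, then c = u × f. With u = 10% and f = 1, c = 10% and power is 71.6%. With u = 10% and f = 0.5, c = 5% and power is 76.1%. Reading c as the plain share of users (f = 1) therefore gives the largest loss for that share.

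**The case against.** **The control arm is defined and checked.** The abstract says controls receive only standard coaching, and the monthly call covers adherence in both arms. For a control, adherence could naturally be read as coaching without the band. This stands in part: it would be wrong to infer that controls are not followed up on adherence at all. But the call's content for controls is not written down, and neither the abstract nor section 6(f) says whether a patient's own device counts.

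**The consent pages are not in the available text.** An instruction to controls could be there. This stands, and it limits the finding to what the visible sections contain.

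**Background use may belong in the comparator.** The intervention is the supply of a particular band, app and education on top of usual care. Section 2 describes measurement more frequent than these patients would usually have. On that pragmatic reading, a control's own scale is part of usual care, and barring it would change the question. Aim i speaks of use, which points the other way, but the text does not settle it. This is why excluding every home-scale user cannot be called a necessary correction. Recording use is needed on either reading.

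**The loss is hypothetical.** No rate of use is given, and wearable bioimpedance is described as recent. A home scale without the app, the education and the weekly instruction need not match the band. This stands, and it makes the power figures a range of possibilities.

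**The Table I footnote is weak evidence.** A footnote reads "Only for study group", but in the text as extracted its marker is attached to the surgical-outcomes row. The point rests on the position of the compliance row in the wearable-group block and does not rely on the footnote.

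**Conclusion.** The gap is real and modest. The visible protocol neither asks about nor records patients' own devices, gives controls no stated device rule, and leaves the content of their monthly call open. The plan reproduces at 80.3% power with almost no slack, so a 10% loss of contrast would leave 72% and a 20% loss 61%. These figures assume a two-sided 5% test, the plan's own SD and correlation, and an assumed c. They are worst cases if c is read as the share of controls using a device.

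A reader might infer three stronger things that the documents do not support:
- That the trial is underpowered because of crossover. No rate of device use is given, so this is a risk and not an established loss. Use that predates randomisation is also not crossover, and it can occur in either arm.
- That enrolling current device users is an eligibility error. It is one only if aim i means the effect of use rather than of supply.
- That dilution always favours a noninferiority claim. It does so when the tested arm is truly worse. If the band helps and the band arm is the one tested, dilution erodes its advantage. Section 10 does not state the direction.

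The firm conclusion concerns interpretation: without a record of device use, a null result could not be attributed to the band.

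**What to change.** 1. Add one question to the existing screening questions: does the patient currently use a wearable or home device that reports body fat or muscle mass? Keep the answer for enrolled patients.
2. Ask the same question of both arms on the monthly calls already planned, and record it where the blinded PI does not see it.
3. In section 6(f)(i)(2), state that controls are asked not to start a wearable bioimpedance device during the coaching period.
4. In section 10, report device use by arm, keep the primary analysis by randomised arm, and add a sensitivity analysis without patients who used a device at baseline. That subset is defined before randomisation, so the comparison stays randomised. Dropping patients who started a device later would not have that property.
5. State whether aim i concerns use of the band or its supply on top of usual care. If it is use, excluding current users of wearable bioimpedance is reasonable. Excluding all home-scale users is optional.

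The cost is one extra question, a small request to controls and, if current wearable users are excluded, possibly a few patients not enrolled. Device use that is not recorded as it happens cannot be recovered reliably afterwards.
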